4. EVALUATION TIMELINE

Please include a timeline for key activities of the evaluation below. Example of activities may include IRB submission, staff training, waves of data collection, analysis period, and report writing and submission.

Evaluation Activity	Start Date	End Date
Hire Evaluation Staff : Project Manager (Senior Consultant), CQI Data Manager (CQI-DM)	1/15/2021	2/15/2021
Evaluation Staff Training : Performance Data Measurement and Management (PDMM), CQI Process, Study Activities, Evaluation Plans	1/22/2021	3/12/2021
Kickoff Meeting : introduce evaluation team to project staff and orient them to study activities	2/3/2021	2/28/2021
IRB Certification : evaluation and project staff complete human subjects training	10/1/2020	2/28/2021
Evaluation Plan : evaluation and project staff develop and submit evaluation plan	1/15/2021	2/19/2021
Survey Tools : evaluation staff develop OLLE Pre/Follow-up Surveys (nFORM items at baseline included on OLLE Follow-up)	10/1/2021	2/28/2021
IRB Approval : evaluation staff develop and submit relevant documents to Solutions IRB	3/1/2021	3/15/2021
CQI Team : form team and conduct ongoing bi-weekly meetings to start CQI Process	3/15/2021	7/1/2025
CQI Training : train the CQI-DM and CQI Team about PDMM and the CQI Process	1/22/2021	3/19/2021
Study Activities Training : present to project staff an IRB approved study protocol for consent, enrollment, and data collection.	3/1/2021	3/28/2021
Implementation Evaluation : collect nFORM data to track delivery of intended service amounts	05/1/2021	05/01/25
Baseline Surveys : ACS, nFORM Entrance, OLLE Pre	5/1/2021	05/31/24 for local evaluation surveys; nFORM surveys will continue as required by

		federal funder until conclusion of program services
Exit Surveys : nFORM Exit, OLLE Post	8/1/2021	08/01/24
Follow-up Surveys : OLLE Follow-up (with items from nFORM Entrance)	5/1/2022	05/31/25
Preliminary Implementation Report Submitted	5/31/2022	6/31/2022
1 st Manuscript submitted for publication	7/1/2025	12/31/2025
Final Report Submitted	04/1/2024	06/01/2025 for first draft with final report to be submitted before the conclusion of the grant cycle

* you may add rows by hitting the tab button, or right click and select insert row below

EVALUATION PLAN

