I4	To what extent did the CQI Team carry out the steps in the CQI Plan each program year?	Implementation
R1	What is the impact of enhanced TCD services (treatment) compared to standard TCD services only (control) on healthy parenting attitudes immediately following program completion?	Outcome
R2	What is the impact of enhanced TCD services (treatment) compared to standard TCD services (control) only on healthy partner relationship behaviors 6 months after TCD enrollment?	Outcome
R3	What is the impact of enhanced TCD services (treatment) compared to standard TCD services only (control) on healthy parenting behavior 6 months after TCD enrollment?	Outcome
R4	What is the impact of enhanced TCD services (treatment) compared to standard TCD services only (control) on healthy co-parenting behavior 6 months after TCD enrollment?	Outcome
R5	Does the impact of the Ray of Hope hours vary by ethnicity?	Secondary outcome

* you may add rows by hitting the tab button, or right click and select insert row below

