1.2. OUTCOME RESEARCH QUESTIONS

For each outcome research question listed above, whether a descriptive or impact design, summarize the inputs (e.g., program components, program supports, implementation features, etc.), target population (e.g., the population for which the effect will be estimated) and the outcomes (e.g., child well-being, father-child engagement, etc.) that will be examined to answer the research question(s). Comparisons for descriptive evaluations may reflect circumstances before the grant, pre-treatment, or pre-determined benchmark from other studies with similar interventions.

Research Question Number	Intervention	Target Population	Comparison	Outcome	Confirmatory or Exploratory?
R1	Ray of Hope curriculum (10 hours) that focuses on domestic violence and related risk factors	Latino fathers: low-income, 18+ years, no open criminal cases (or deferred), children up to 24 years	Parenting attitudes for the treatment group to the control group immediately after completing TCD program.	Healthier parenting attitudes for the Treatment Group that receives enhanced services.	Confirmatory
R2	Ray of Hope curriculum (10 hours) that focuses on domestic violence and related risk factors	Latino fathers: low-income, 18+ years, no open criminal cases (or deferred), children up to 24 years	Partner relationship behaviors for the treatment group to the control group 6 months after TCD enrollment.	Healthier partner relationship behaviors for the Treatment Group that receives enhanced services.	Confirmatory
R3	Ray of Hope curriculum (10 hours) that focuses on domestic violence and related risk factors	Latino fathers: low-income, 18+ years, no open criminal cases (or deferred), children up to 24 years	Parenting behavior for the treatment group to the control group 6 months after TCD enrollment.	Healthier parenting behavior for the Treatment Group that receives enhanced services.	Confirmatory
R4	Ray of Hope curriculum (10 hours) that focuses on	Latino fathers: low-income, 18+ years, no open criminal	Co-parenting behavior for the treatment group to the	Healthier co-parenting behavior for the Treatment	Confirmatory

	domestic violence and related risk factors	cases (or deferred), children up to 24 years	control group 6 months after TCD enrollment.	Group that receives enhanced services.	
--	--	--	--	--	--

* you may add rows by hitting the tab button, or right click and select insert row below

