10. DATA COLLECTION

10.1. CONSTRUCTS AND MEASURES

Clearly articulate the constructs of interest, measures to evaluate those constructs, and specific data collection instruments. Provide any information on the reliability and validity of the data collection instruments. For standardized instruments, you may provide the citation for the instrument.

Measure	Sample	Variable Type	Data source(s)	Variable Name	Definition
Co-parenting relationship behaviors	Has at least one child age 24 or younger	Continuous (range from 1 to 5 where 1 is strongly disagree and 5 is strongly agree)	nFORM entrance, OLLE follow-up	Copar_Beh	Average of 11 survey items that relate to positive interactions with the mother of participant's youngest child
Parenting relationship behaviors	Has at least one child age 24 or younger, saw child within past month	Continuous (range from 1 to 5 where 1 is never and 5 is every day or almost every day)	nFORM entrance, OLLE follow-up	Par_Beh	Average of 10 to 11 survey items (depending on child age) that relate to frequency of positive interactions with participant's youngest child
Parenting relationship attitudes	Has at least one child age 24 or younger, saw child within past month	Continuous (range from 1 to 5 where 1 is always and 5 is never)	nFORM entrance, nFORM exit	Par_Att	Average of 6 survey items that relate to frequency of feelings about participant's youngest child
Parenting relationship behaviors	Has at least one child age 24 or	Continuous (range from 1 to 5 where 1 is	nFORM entrance, ,	Parent_Fight	Reported frequency of

	younger, saw child within past month	never and 5 is every day or almost every day)	OLLE follow-up		fighting with child
Partner relationship behaviors	All survey respondents	Continuous (range from 1 to 5 where 1 is never and 5 is always)	OLLE pre-survey, OLLE post-survey, OLLE follow-up	Partner_Fight	Reported frequency of fighting with partner
Partner relationship behaviors	All survey respondents	Continuous (range from 1 to 5 where 1 is never and 5 is always)	OLLE pre-survey, OLLE post-survey, OLLE follow-up	Partner_Disagree	Average of 7 survey items related to frequency of disagreement with partner on different topics

* you may add rows by hitting the tab button, or right click and select insert row below

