10.3. METHODS OF DATA COLLECTION

If the evaluation will collect multiple waves of data, describe the timing of these waves below. When describing follow-up periods, specify whether the follow-up period will be post-baseline, post-random assignment, or post-program completion.

Wave of Data Collection (e.g., baseline, short-term follow-up, long-term follow-up)	Timing of Data Collection
Baseline	Collected immediately following informed consent and enrollment – during orientation or before first primary workshop session
Post-test	Collected after the completion of the primary services programming – during or following the last workshop or session
Follow-up (6 months after enrollment)	Collected approximately six months after program enrollment

For each measure, describe how data will be collected detailing which data collection measures will be collected by which persons, and at what point in the programming or at what follow-up point.

Measure	Timing of Data Collection (baseline, wave of data collection)	Method of Data Collection	Who Is Responsible for Data Collection?	Impact Evaluations Only: Will Methods or Collection Procedures Differ by Study Group?	Administrative Data Only: Will data access require data sharing agreement?
On-line Local Evaluation (OLLE) and nFORM Baseline Survey	Baseline	Participant self-enters survey using online data collection program or on paper surveys if necessary	CQI Data Manager will proctor data collection and assist participants as necessary	No	
OLLE and nFORM Post-Test Survey	Post-Test (approx. 12 weeks after enrollment during last workshop session)	Participant self-enters survey using online data collection program or on paper surveys if necessary	CQI Data Manager will proctor data collection and assist participants as necessary	No	
OLLE Six Month Follow-up Survey	Six months after enrollment / baseline	Participant self-enters survey using online data collection platform and link – or – Phone interview data collection	MER Research Staff/ participant tracking team	No	

* you may add rows by hitting the tab button, or right click and select insert row below

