10.4. ENSURING AND MONITORING DATA COLLECTION

Describe plans for training data collectors and for updating or retraining data collectors about procedures. Detail plans to regularly review data that have been submitted and to assess and swiftly address problems.

This evaluation will utilize both post-program surveys (completed at the completion of core programming) and follow-up surveys collected six months after enrollment. The methods for these data collections differ. The primary driver for post-program survey completion is high rates of program retention. This data point will be collected during the last workshop session. As such, only those individuals who complete the program and who are at the data collection session will be likely to participate in the post-program data collection.

All program staff and evaluation staff will undergo a rigorous set of trainings to prepare for the evaluation. All staff receive an overview and introductory training to present the goals and objectives of the evaluation effort and its importance to the overall project. Next, all staff receive training on human subject protection and are required to pass a certification test on the subject matter. All staff will also receive a detailed training on the evaluation, including the evaluation tools, timing and data collection process, and the role and importance of randomization of participants.

In addition, the data manager and the primary local evaluation staff will undergo a rigorous training process to better understand the context of HMRF research, training on data collection procedures they will be responsible for, and training on the nFORM system and use of nFORM data in a CQI process. MER is creating networks of CQI data managers and Evaluation Project Managers across the 12 projects that we are evaluating so that all staff have access to experienced data managers and evaluation staff who have done this work previously. This training takes the form of weekly training sessions that are currently underway.

Members of the CQI team will also receive specific training on the MER CQI process that has been developed prior to the launch of data collection or program services. As described elsewhere, MER is assisting the program staff in implementing a robust CQI process that will focus on retention as one of the primary areas of program improvement, and as such, we are anticipating relatively modest levels of attrition for this data collection.

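### R1 (parenting attitudes) rests on an exit survey answered in effect by program completers, so as planned it compares completers and does not show that randomisation isolates the effect

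*Protocol*

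**What the plan says.** **Status and timing of R1.** Protocol 1.1 asks for the effect "on healthy parenting attitudes immediately following program completion". Protocol 1.2 sets the comparison as "Parenting attitudes for the treatment group to the control group immediately after completing TCD program" and marks it confirmatory. The SAP (Analytic approach) instead lists parenting attitudes as the secondary outcome.

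**Source.** The measure tables in Protocol 10.1 and in the SAP give Par_Att the sources "nFORM entrance, nFORM exit". The other parenting, co-parenting and partner measures all list the OLLE follow-up; Par_Att does not. One sentence in the SAP's Analytic approach bases primary and secondary estimates alike on the follow-up survey, but the rest of that section places attitudes at program completion.

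**Who answers.** Protocol 10.4 says of the post-program survey: "This data point will be collected during the last workshop session". It adds that "only those individuals who complete the program and who are at the data collection session will be likely to participate". Protocol 10.3 words the wave as "Collected after the completion of the primary services programming – during or following the last workshop or session", puts it about 12 weeks after enrolment, and says procedures do not differ by study group.

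**Handling of non-response.** The SAP sample requires an entrance survey plus an exit and/or follow-up survey. Missing outcomes are not imputed. A response analysis is planned for each primary outcome, including a look at response by arm. Its complete-case category is a pre-survey plus a follow-up survey.

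**The claim.** Protocol section 5 says random assignment will isolate the effect of Ray of Hope on parenting attitudes.

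**The concern.** Randomisation makes the 443 fathers assigned to each arm comparable. It does not make comparable the subsets who stay to the end, because staying is a behaviour after assignment and may be related both to the arm and to attitudes. If the fathers who stay differ between arms, a difference in Par_Att can appear with no effect of Ray of Hope, or a real effect can be hidden. R1 as worded also has no defined value for a father who does not complete.

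The six-month wave lists an online link, phone interviews, a tracking team and a $50 card. For the exit wave the protocol lists proctored online or paper completion and no survey payment. So the outcome most dependent on retention has the least effort described for reaching fathers who leave.

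At stake is whether a positive R1 result can be credited to the curriculum or only describes who remained.

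**Working it through.** **1. Does the SAP repair the selection?** Three provisions bear on it.
- Complete-case analysis without imputation drops every father with no exit survey.
- The response analysis covers primary outcomes, and the SAP calls attitudes secondary, so R1 may fall outside it. Its three categories (no survey after the ACS, pre-survey only, pre- and follow-up survey) contain no group of exit respondents. It aims to adjust for threats to validity but names no method.
- Covariates enter the model only where baseline differences are detected. That does not address selection on unmeasured motivation.

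**2. Where does the exit survey fall relative to Ray of Hope?** Protocol section 1 names TYRO Dads and Core Communication as the primary services, and section 7 says both arms attend these together on one schedule. Section 10.3 describes the wave as "Collected after the completion of the primary services programming", and 10.4 ties it to core programming. R1 is worded by program completion, and only the treatment arm has the further 10 hours. Two readings remain:
- If the survey follows Ray of Hope, the burden of reaching it may differ by arm.
- If it closes the shared services, the burden is the same, but some treatment fathers may answer before Ray of Hope ends.

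**3. The plan's own figure.** Inputs from Protocol 9.2 and 9.3: 443 assigned and 310 analysed per arm, one-tailed 0.05, 80% power, MDES 0.2.
- MDES = (1.645 + 0.842) × √(2/310) = 0.1997, so the stated 0.2 reproduces.
- Planned loss is 443 − 310 = 133 per arm (30.0%), equal in both arms. This allows for lost precision, not for selection. No response rate is given for the exit wave itself.

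**4. Illustration under assumptions.** There is no true effect and the outcome SD is 1. A father answers if a normal latent trait, correlated ρ with attitude, exceeds a cut-off. Response is p_C in control and p_T in treatment. The documents give neither the exit response by arm nor ρ; p_C = 0.70 borrows the overall 310/443.
- λ(p) = φ(Φ⁻¹(1 − p))/p, so λ(0.60) = 0.6439, λ(0.65) = 0.5698, λ(0.70) = 0.4967 and λ(0.75) = 0.4237.
- Bias = ρ × [λ(p_T) − λ(p_C)].
- SE = √(1/(443 p_T) + 1/(443 p_C)).
- One-sided rejection = 1 − Φ(z − bias/SE), with z = 1.645 at 0.05, or 2.394 at 0.05/6 = 0.83% (the SAP's Bonferroni correction over six outcomes, taken as one-sided).

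For p_T = 0.60 and ρ = 0.3: bias = 0.3 × (0.6439 − 0.4967) = 0.044 SD, SE = 0.0836, ratio 0.528.

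| p_C | p_T | ρ | Bias (SD) | Rejection at 0.05 | Rejection at 0.05/6 |
|---|---|---|---|---|---|
| 0.70 | 0.70 | any, same in both arms | 0 | 5.0% | 0.83% |
| 0.70 | 0.65 | 0.3 | +0.022 | 8.4% | 1.7% |
| 0.70 | 0.60 | 0.3 | +0.044 | 13.2% | 3.1% |
| 0.70 | 0.60 | 0.5 | +0.074 | 22.2% | 6.5% |
| 0.70 | 0.75 | 0.3 | −0.022 | 2.7% | 0.4% |

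Equal response rates alone do not guarantee zero bias. At 70% in both arms with ρ = 0.3 in treatment and 0.2 in control, bias = 0.1 × 0.4967 = 0.050 SD.

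**The case against.** The strongest reply is that nothing in the documents makes completion harder in the treatment arm. The post-test can be read as closing the shared curricula, which both arms attend together. It is planned at about 12 weeks for everyone, with identical procedures, and the sample-size table projects equal retention. This stands. A reader might infer from the extra 10 hours that finishing asks more of treatment fathers and so biases R1 in favour of Ray of Hope. No section says so, completion is never defined by arm, and the bias could run either way.

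A reader might also infer that a father who leaves cannot supply an R1 outcome at all. That goes beyond the text. Section 10.4 speaks of likelihood, and 10.3 allows collection after the last session.

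The SAP does plan a response analysis by arm and a Bonferroni correction. The correction lowers the absolute error rates considerably, though in the positive-bias rows they remain above the nominal 0.83%. The one-tailed test appears only in the power table; the SAP states p < .05 without sides. The response analysis, as written, does not reach the exit wave.

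What survives the reply is that the R1 sample is selected after randomisation, and the plan has no analysis that brings the other randomised fathers back in.

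**Conclusion.** The concern holds in a limited form. R1 as planned is in effect a comparison among fathers who completed and were present, and it does not support the claim that random assignment isolates the effect on attitudes. The exit survey's place relative to Ray of Hope is ambiguous and must be reconciled, as must the confirmatory and secondary labels.

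That R1 is actually biased, or biased towards treatment, is not established. Under the assumed gaps of 5 to 10 points in response and correlations of 0.3 to 0.5, the bias is about 0.02 to 0.07 SD, against an MDES of 0.2. With equal response and equal selection it is zero, and the estimate then still describes completers only. This affects the interpretation of one of four confirmatory questions; R2 to R4 use the six-month wave.

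**What to change.** (a) **Time point.** Define R1 at one time from enrolment, identical in both arms (Protocol 10.3 already gives about 12 weeks), and state where the exit survey falls relative to Ray of Hope. For any father still reachable in that window, seek the six Par_Att items whatever his attendance, by the link and phone route used at six months. The scope is narrow: the SAP is dated 12/9/2024 and study enrolment ended 11-30-2024, so only fathers enrolled from about mid-September 2024 would still have been within 12 weeks.

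(b) **Analysis.** Extend the response analysis to the exit wave and report exit response by arm. Pre-specify an all-randomised sensitivity analysis of R1 by inverse-probability weighting or multiple imputation, using baseline Par_Att and ACS covariates, with a check on departures from missing at random. Protocol section 4 describes the follow-up as carrying baseline items ("nFORM items at baseline included on OLLE Follow-up"). If the six attitude items are among them, use them as supportive evidence only, since six months is a different time point from the R1 question.

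(c) **Reporting.** If exit data remain limited to completers, report R1 as a comparison among completers and drop the claim that randomisation isolates the effect. Settle whether R1 is confirmatory or secondary.

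**Cost.** Part (a) needs some added contacts by the existing tracking team and possibly an IRB amendment. Part (b) needs SAP text and a few further models on data the plan already collects. Part (c) needs wording only. The downside is a possibly weaker R1 conclusion.

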11. IRB/PROTECTION OF HUMAN SUBJECTS

Please describe the process for protection of human subjects, and IRB review and approval of the proposed program and evaluation plans. Name the specific IRB to which you expect to apply.

Solutions IRB, a private commercial Association for the Accreditation of Human Research Protection Programs Inc. (AAHRPP) fully accredited Institutional Review Board, will ensure that this study is approved before any research activities take place. MER has had 14 research studies approved by Solutions IRB over the past four years, has completed over 15 annual check-in reports, and has submitted timely amendments when changes to studies needed to take effect.

All submissions are completed online, so turnaround for a new study approval is between 24 to 72 hours, though the full approval process can take approximately one to two weeks depending on the number of questions and requested revisions that the IRB makes. In the IRB application submission, we will include descriptions of project staff, locations of study sites, the funding source, incentives, summary of activities, participant population, recruitment plans, risks and benefits, confidentiality of data, and the informed consent process along with all materials to be used in the study such as participant forms and surveys.

This project will be submitted for IRB approval in early March 2021 to receive official approval to begin enrollment and data collection that begin on April 1, 2021.

12. DATA

12.1. DATABASES

For each database used to enter data, please describe the database into which data will be entered (i.e., nFORM and/or other databases), including both performance measure data you plan to use in your local evaluation and any additional local evaluation data. Describe the process for data entry (i.e., who will enter the data into the database).

Database Name	Data Entered	Process for Data Entry
nFORM	Participation Data, Participant Outcomes (nFORM Surveys-ACS, Entrance, Exit), Workshop attendance, case management	Entered directly by TCD participants and TCD Project staff
Qualtrics	Participant outcomes (OLLE survey)	Entered directly by participants and MER staff

* you may add rows by hitting the tab button, or right click and select insert row below

